### 1.3 FLOW CHART FOR OPEN LABEL EXTENSION PERIOD, FIRST 96 WEEKS

	Transition to open label	Open Label Treatment Period b																	
Week (W) a	Transition	W4	W8	W12	W16	W20	W24	W30	W36	W42	W48	W54	W60	W66	W72	W78	W84	W90	W96
Visit number s	1	2	3	4	5	6	7	8	9	10	11	12	13	14	15	16	17	18	19
Entry procedures																			
Informed consents e and assent	X																		
Efficacy																			
EDSS/FS							X				X				X				X
SDMT							X				X				X				X
Cognitive tests f																			X
Brain MRI p											X								X
Safety																			
Adverse event reporting f		<----->																	
Vital signs g	X	X	X	X			X		X		X		X		X		X		X
Physical examination t				X			X				X				X				X
ECG 12-leads																			
Tanner h							X				X				X				X
Clinical routine laboratories i,j	X	X		X			X		X		X		X		X		X		X
Clinical safety laboratories i,k,n			X		X	X		X		X		X		X		X		X	
Immunoglobulins / TSH																			X
Treatments																			
Concomitant medications	X	X		X			X		X		X		X		X		X		X
Dispense study drugs/IVRS call	X		X	X			X		X		X		X		X		X		X
Accountability / compliance			X	X			X		X		X		X		X		X		X
Teriflunomide PK sampling l		XXX	X	X			X		X										

### 1.4 FLOW CHART FOR OPEN LABEL PERIOD, CONTINUED

	Open Label Treatment Period b																Post drug elimination follow up		Unscheduled
Week (W) a	W102	W108	W114	W120	W126	W132	W138	W144	W150	W156	W162	W168	W174	W180	W186	W192/ EOT c,v	EOT +2W	EOT +4W	Relapse visit
Visit number	20	21	22	23	24	25	26	27	28	29	30	31	32	33	34	35	36 c	37 c	
Entry procedures																			
Informed consents e and assent																			X
Efficacy																			
EDSS/FS				X				X				X				X			X o
SDMT				X				X				X				X			
Cognitive tests f																X			
Brain MRI p								X								X			
Safety																			
Adverse event reporting f	←----->																		
Vital signs g		X		X		X		X		X		X		X		X	X	X	X
Physical examination t				X				X				X				X	X		
ECG 12-leads																X	X q	X q	
Tanner h				X				X				X				X			
Clinical routine laboratories i,j		X		X		X		X		X		X		X		X			
Clinical safety laboratories i,k,n	X		X		X		X		X		X		X		X		X	X	
Immunoglobulins / TSH																X			
Treatments																			
Concomitant medications	X	X	X	X	X	X	X	X	X	X	X	X	X	X	X	X	X	X	X
Dispense study drugs/IVRS call		X		X		X		X		X		X		X		X u			
Accountability / compliance		X		X		X		X		X		X		X		X			
Teriflunomide PK sampling l																X	X m	X m	

EOT = end of treatment (EOT= First visit after last study drug intake), EDSS = expanded disability status scale, FS = functional score, BVMT-R = brief visuospatial memory test-revised, SDMT=symbol digit modalities test, MRI = magnetic resonance imaging, PK = pharmacokinetic

- a The open label period starts by the transition visit. It is recommended that there is no time gap between the 2 periods, or as short as possible and if possible less than 2 weeks. In case of start of the open label period at the end of the 96 weeks of the double-blind period, the transition visit will generally coincide with the EOT visit of the double-blind period. Recommended windows: The window for obtaining biological samples at any given visit will be  $\pm 7$  days. All other treatment period assessments should be completed within  $\pm 7$  days of the scheduled visit date relative to the transition visit. Post drug elimination follow-up visits should be  $\pm 7$  days of scheduled visit relative to end of treatment.
- b For a regional or national emergency declared by a governmental agency, contingency measures are included in [Section 17.7](#)
- c End-of-treatment and premature discontinuation visit.
- d For patients discontinuing treatment, 2 post drug elimination follow up visits should be scheduled 2 weeks and 4 weeks after study medication discontinuation and initiation of the drug elimination procedure. When applicable patients who prematurely and permanently discontinue study medication will be asked to continue until the planned end of double-blind period (ie, 96 weeks after randomization)
- e Re-consent before starting open-label period and after confirmed MS relapse and when patients turn adults as per local regulations.
- f During the adverse event reporting process, specific questions about pulmonary symptoms and peripheral neuropathy symptoms will be asked. (Patients will be instructed to alert the treating physician of symptoms suggestive of immunodeficiency)
- g Including systolic and diastolic blood pressure, heart rate, body temperature, weight and height; patient standing in bare or stocking feet. Height and weight is to be documented in the growth charts –Blood pressure (BP) and heart rate to be measured in both the supine and the standing positions (measures taken 3 minutes after supine and 3 minutes after standing). A sphygmomanometer with a blood pressure cuff appropriate to the patient's arm girth is used. Of note, during remote visits, only weight will be collected.
- h Tanner stage to be assessed at every 24 weeks and EOT for all patients (until complete sexual maturity).
- i Pancreatic ultrasound must be performed if there are clinical or lab abnormalities suggesting pancreatitis or enzymes elevation  $\geq 3 \times$  ULN and must be followed up with a computed tomography (CT) with contrast or MRI
- j The following routine parameters will be measured at transition visit if previous laboratory assessment was performed more than 4 weeks before, at Weeks 4, 12, 24, 36, 48, then every 12 weeks and at EOT: Hematology and differential panel (hemoglobin, hematocrit, red blood cell count and red blood cell morphology, mean corpuscular volume, white blood cell count, neutrophils, lymphocytes, monocytes, eosinophils, basophils, platelets); Coagulation panel (prothrombin time, and activated partial thromboplastin time); Complete chemistry panel (glucose, creatinine, blood urea nitrogen (BUN), sodium, potassium, chloride, bicarbonate, magnesium, calcium uric acid, aspartate aminotransferase (AST), alanine aminotransferase (ALT), gamma-glutamyl transpeptidase (GGT), lactate dehydrogenase (LDH), total bilirubin, direct/indirect bilirubin, alkaline phosphatase, inorganic phosphorus, total protein, albumin, globulin, albumin/globulin ratio, triglycerides, cholesterol and creatine phosphokinase (CPK). Pancreatic enzymes (serum amylase and lipase); Urinalysis (pH, ketones, protein, glucose, blood, urobilinogen, bilirubin, microscopic sediment, specific gravity). For pubescent females serum pregnancy test  $\beta$ - Human chorionic gonadotropin; ( $\beta$ -HCG) will be performed every 12 weeks
- k The following safety laboratory tests will be conducted in between clinical routine lab at Weeks 8, 16, 20, 30 and then every 12 weeks up to the end of treatment (EOT). Study nurse visit at patient's home can be provided (except at Week 8). In addition at EOT+2 weeks and EOT+4 weeks. The following safety laboratory testing will be conducted: (measuring hematology and differential panel [as above], liver function tests [ALT, AST, GGT, total bilirubin, and direct/indirect bilirubin] and pancreatic enzymes [serum amylase and lipase]). In addition, uric acid and inorganic phosphorus will be done at EOT+2 weeks and EOT+4 weeks.
- l PK samples will be collected at Week 2, 3, and 4 (PK run-in (8 weeks) period); an additional 4th sample may be required in case of inadequate sampling or information/variability from 3 samples. Study nurse visit at patient's home can be provided when PK sampling is not synchronized with routine lab visit (W2, W3 or in the event the 4th sample is needed).
- m Post drug elimination procedure: samples to be collected for verification of plasma teriflunomide concentrations  $\leq 0.02 \mu\text{g/mL}$
- n In addition if a patient has a vaccination, antibody titers will be assessed before and after vaccination (inactivated vaccines only)
- o EDSS required also after each clinical relapse, to be performed within 7 days.
- p If patient is treated with steroids the MRI should be performed after 14 days discontinuation of the steroids
- q ECG should be performed only for patients who had new abnormalities on the EOT ECG; or when ECG could not be performed at EOT (in exceptional circumstances).
- r Cognitive Battery Tests: TMT-A and B, SRT, Beery VMI, BVMTR, D-KEFS Fluencies (Letter and Category); BVMTR and WASI Vocabulary potentially supplemental. When available
- s The number of visits is linked to the time in the previous double blind phase as the maximum period in the study is 192 weeks. The maximum potential duration is therefore 184 weeks
- t The date of the menarche should be captured if applicable
- u IVRS only if treatment is stopped
- v An optional additional extension period with teriflunomide is offered to young patients, to provide them treatment until they are 18 years old and/or can switch to commercial product, whichever comes first.

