- h* Including systolic and diastolic blood pressure, heart rate, body temperature, weight and height (Height only at V2 and EOT); patient standing in bare or stocking feet. Height and weight is to be documented in the growth charts –Blood pressure (BP) and heart rate to be measured in both the supine and the standing positions (measures taken 3 minutes after supine and 3 minutes after standing). A sphygmomanometer with a blood pressure cuff appropriate to the patient's arm girth is used.
- i* Tanner stage to be assessed at baseline, every 24 weeks and at EOT for all patients (until complete sexual maturity).
- j* Pancreatic ultrasound must be performed if there are clinical or lab abnormalities suggesting pancreatitis or enzymes elevation  $\geq 3$  x ULN and must be followed up with a computed tomography (CT) with contrast or MRI in case of ultrasound with abnormal pancreatic findings
- k* The following routine parameters will be measured at screening, randomization, Weeks 4, 12, 24, 36, 48, then every 12 weeks and at EOT: Hematology and differential panel (hemoglobin, hematocrit, red blood cell count and red blood cell morphology, mean corpuscular volume, white blood cell count, neutrophils, lymphocytes, monocytes, eosinophils, basophils, platelets); Coagulation panel (prothrombin time, and activated partial thromboplastin time); Complete chemistry panel (glucose, creatinine, blood urea nitrogen (BUN), sodium, potassium, chloride, bicarbonate, magnesium, calcium uric acid, aspartate aminotransferase (AST), alanine aminotransferase (ALT), gamma-glutamyl transpeptidase (GGT), lactate dehydrogenase (LDH), total bilirubin, direct/indirect bilirubin, alkaline phosphatase, inorganic phosphorus, total protein, albumin, globulin, albumin/globulin ratio, triglycerides, cholesterol and creatine phosphokinase (CPK). Pancreatic enzymes (serum amylase and lipase); Urinalysis (pH, ketones, protein, glucose, blood, urobilinogen, bilirubin, microscopic sediment, specific gravity). For pubescent females serum pregnancy test  $\beta$ - Human chorionic gonadotropin; ( $\beta$ -HCG) will be performed at screening, randomization and then every 12 weeks

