#### **9.5 ULTRA SOUND OF THE PANCREAS**

An ultrasound will be performed for patients with confirmed pancreatic enzymes elevation  $\geq$ 3 x ULN and/or symptoms suggestive of pancreatitis.

The ultrasound examination will be performed according to local standards. A gastroenterologist will review the report and provide clinical conclusion. Abnormal findings should be reported as AEs.

All ultrasounds with abnormal pancreatic findings must be followed by a CT scan with contrast or MRI of the pancreas and report added to the CRF.

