#### **10.1.4 Post drug elimination follow up visits**

Two post-washout follow up visits should be scheduled 2 weeks and 4 weeks after study medication discontinuation and initiation of the washout procedure. These visits are not required in case the patient receives commercial product immediately after the study end.

The following items will be checked/performed and recorded at Visit 21 (EOT+2W) and Visit 22 (EOT+4W):

- Adverse events reporting.
- Concomitant medications.
- Vital signs (BP, HR, body temperature and weight).
- Physical examination at EOT + 2 Weeks only.
- ECG should be performed only for patients who had new abnormalities on the EOT ECG.
- Clinical safety laboratories
  - Hematology and differential panel,
  - Liver function panel,
  - Pancreatic enzyme tests,
  - Uric acid and inorganic phosphorus.
- Post-washout PK sampling (note that the EOT+4W PK sample should be taken even if the EOT+2W PK sample is under 0.02 µg/mL, to document stability level as per EU SmPC).

In case of adverse events AE/abnormal laboratory values, or teriflunomide level > 0.02 µg/mL after the elimination treatment, follow up until resolution should be planned.

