### **10.1.5 Open Label Period**

Procedures are described in the specific flow chart [Section 1.3](#), [Section 1.4](#), [Section 1.5](#), and in [Section 17.7](#).

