## **REASON FOR AMENDED PROTOCOL 3 (02 August 2018):**

The efficacy and safety of teriflunomide are evaluated in children with pediatric multiple sclerosis (MS) in Study EFC11759/Terikids, which is ongoing. The enrolment in the study is completed. Teriflunomide is currently approved in countries participating in this study for the treatment of adult patients with relapsing remitting multiple sclerosis (RRMS). At the end of their participation in the study, some patients will be too young to access commercial teriflunomide as per authorized indication. This open-label optional additional extension period may be considered for such patients. The optional additional extension period will assess the continued safety and efficacy of teriflunomide in patients until they are 18 years old and/or are able to switch to commercial teriflunomide in their country, whichever comes first. It will be implemented in France, and possibly other countries, where local solutions for continued teriflunomide treatment are not possible within a reasonable time frame.

The optional additional extension period will be performed in conditions approaching clinical practice. In this perspective, the dose will be decided by the Investigator without knowledge of the dose in the study. This is necessary to ensure blinding and integrity of the core study, and it is similar to what is done for young patients who receive marketed Aubagio at the end of the study in the context of local country specific solutions. The recommended dose will be teriflunomide 14 mg for patients >40 kg, in continuation to the open-label period of the study, in which the

maintenance dose is 14 mg adult equivalent and is expected to be usually 14 mg. This is supported by the good safety of teriflunomide in the study up to now. If the investigator considers that a lower dose would be more appropriate, in particular for patients <40 kg (which is expected to be infrequent, as patients' age will be  $\geq 14$  years old), it is possible to administer teriflunomide 14 mg with a lower frequency, eg, every other day for an equivalent of 7 mg.

The safety of teriflunomide is being continuously monitored in the Study EFC11759/Terikids. Regular safety reviews have been performed by an independent external Data Monitoring Committee (DMC). No major safety issues have been identified since the beginning of the study.

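### The open-label flow chart requires CT or MRI after every triggered pancreatic ultrasound, while the double-blind chart and section 9.5 require it only after an abnormal one

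*Protocol*

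**What the plan says.** The rule appears in three places in the protocol and once in the SAP.

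- **Protocol 1.3/1.4, open-label flow charts, footnote i.** After naming the triggers for an ultrasound (clinical or laboratory signs of pancreatitis, or enzymes at least 3 x ULN), the sentence ends: "ULN and must be followed up with a computed tomography (CT) with contrast or MRI". Footnote i is attached to both the routine and the safety laboratory rows.
- **Protocol 1.2, double-blind flow chart, footnote j.** The triggers are the same, but the ultrasound "must be followed up with a computed tomography (CT) with contrast or MRI in case of ultrasound with abnormal pancreatic findings".
- **Protocol 9.5.** "All ultrasounds with abnormal pancreatic findings must be followed by a CT scan with contrast or MRI of the pancreas". This section is not limited to one study period.
- **SAP Appendix C, footnote h.** It repeats the unconditional sentence of footnote i.

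For the open-label period, section 10.1.5 says "Procedures are described in the specific flow chart", and refers sites to the charts in 1.3 to 1.5 and to Appendix G.

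**The concern.** Footnotes i and j are almost the same sentence, except that the open-label one lacks the final condition. As written, every triggered ultrasound in the open-label period leads to mandatory CT with contrast or MRI, including a normal ultrasound. Section 9.5 places no such requirement on a normal ultrasound.

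The participants are children and adolescents. If a site chooses CT, the child receives radiation and contrast that section 9.5 does not ask for. MRI without contrast would also satisfy the footnote. A site that does not scan after a normal ultrasound complies with section 9.5 but deviates from the flow chart.

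The open-label chart is also the one likely to be in use. Section 17.9, in the reason for amended protocol 3 (2 August 2018), states: "The enrolment in the study is completed". By the date of the current version (10 December 2020), the double-blind period should have ended for all patients.

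**Working it through.** The plan gives no figure to reproduce. The check is a comparison of texts, followed by the span over which the rule can operate.

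**1. Texts side by side**

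| Place | Period | Ultrasound trigger | CT or MRI required |
|---|---|---|---|
| Protocol 1.2, footnote j | Double-blind | Suspected pancreatitis or enzymes ≥3 x ULN | If ultrasound abnormal |
| Protocol 9.5 | Not limited | Confirmed enzymes ≥3 x ULN and/or symptoms | If ultrasound abnormal |
| Protocol 1.3/1.4, footnote i | Open-label | As footnote j | After every triggered ultrasound |
| SAP Appendix C, footnote h | Open-label (copy) | As footnote i | After every triggered ultrasound |

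Text lost in PDF conversion is an unlikely explanation, because the SAP copy has the same sentence closed with a full stop after MRI. The amendment history in section 17.9 gives no reason for stricter imaging in the open-label period.

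**2. Duration of the rule per patient**

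- Completers of the double-blind period: 192 − 96 = 96 weeks.
- Earliest switchers, after the 8-week PK run-in: 192 − 8 = 184 weeks. The flow chart agrees: "The maximum potential duration is therefore 184 weeks".

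**3. Scheduled open-label draws that include amylase and lipase** (flow charts 1.3/1.4, footnotes j and k; the conditional transition draw is not counted)

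- Routine, Weeks 4, 12, 24, 36, 48, 60, 72, 84, 96: 9.
- Safety, Weeks 8, 16, 20, 30, 42, 54, 66, 78, 90: 9.
- Through Week 96: 9 + 9 = 18.
- Weeks 102 to 180 every 6 weeks: (180 − 102)/6 + 1 = 14.
- Earliest switcher, with end of treatment at Week 184: 18 + 14 + 1 = 33.
- Footnote k adds two draws after treatment stops ("In addition at EOT+2 weeks and EOT+4 weeks"), giving 18 + 2 = 20 and 33 + 2 = 35. Section 10.1.4 waives them for some patients: "These visits are not required in case the patient receives commercial product immediately after the study end".

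**4. Calendar**

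Assumption: the last patient was randomized by 2 August 2018, or by 30 August 2018 if the 4-week screening period was still running when enrolment was declared complete.

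- Plus 96 weeks: 4 June to 2 July 2020, which is 27 to 23 weeks before 10 December 2020.
- Plus 192 weeks: 7 April to 5 May 2022, which is 69 to 73 weeks after 10 December 2020.

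On these dates no patient was still in the double-blind period when this version was issued, and some could still have more than a year of open-label treatment ahead. The counts show when the rule can be triggered. They do not count scans or measure harm.

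**The case against.** The strongest case against has five parts.

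- **Section 9.5 sets a minimum.** It does not say that CT or MRI is limited to abnormal ultrasounds, so a site that scans every patient satisfies both texts. This is correct: the two instructions can both be followed. They still define different mandatory sets. Section 9.5 requires nothing after a normal ultrasound, and footnote j states the condition expressly.
- **Section 10.1.5 is only a pointer.** The introduction to section 9 sets aside only the optional extension, so section 9.5 does apply in the open-label period. That confirms that both texts are in force, and nothing says which one prevails.
- **The intended rule is inferred.** No passage says that footnote i is a slip. This stands. An omitted clause is the likelier explanation, but if stricter imaging was intended, section 9.5 should say so. A correction is due either way.
- **Imaging feeds two safety rules.** CT or MRI findings lead to expedited reporting (9.8.1) and can require stopping the drug (10.3.2.1). With fewer scans, those criteria would be checked less often. This is a real trade-off, though the criteria themselves do not change and the double-blind period already ran under the conditional rule. A symptomatic child with enzymes above 2 x ULN must stop the drug under 10.3.2.1 without any imaging.
- **The harm is conditional and probably infrequent.** MRI satisfies the footnote, exclusion E 20 removes persistent elevations above 3 x ULN at screening, and section 3.1.2.2 describes pancreatic disorders in adults as low in incidence and balanced. All of this stands and keeps the point minor.

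Section 9.5 also asks for a confirmed elevation before the ultrasound, which neither footnote does. That concerns the trigger and is a separate mismatch.

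**Conclusion.** The concern holds. Two operative protocol texts give open-label sites different instructions on imaging after a normal pancreatic ultrasound, and the chart that section 10.1.5 points to is the stricter one. That the wording differs is certain. That the unconditional version is the mistaken one is an inference from footnote j, section 9.5 and the silent amendment history.

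The number of avoidable scans cannot be stated, because the documents give neither the paediatric rate of triggered ultrasounds nor the share that are normal. The span of the rule rests on the flow-chart schedule, and the calendar on the assumed last randomization date. No endpoint, analysis, sample size or stopping threshold is touched. Severity is minor.

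**What to change.** End footnote i of protocol 1.3/1.4 as footnote j of 1.2 ends, so that the ultrasound "must be followed up with a computed tomography (CT) with contrast or MRI in case of ultrasound with abnormal pancreatic findings". Make the same change in SAP Appendix C, footnote h, for consistency, and notify the sites. Leave the ultrasound trigger, the retest windows and the stopping criteria as they are.

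The cost is one clause in the protocol, the same clause in the SAP copy (which does not direct care) and a site notice. The downside is that CT or MRI after a normal ultrasound becomes a matter of clinical judgement, so pancreatic changes that only CT or MRI would show may be looked for less often. If the sponsor does want imaging after every triggered ultrasound in the open-label period, section 9.5 should be amended to say so, with a reason.

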### 1.5 FLOW CHART FOR OPTIONAL ADDITIONAL EXTENSION PERIOD FOR YOUNG PATIENTS

	Optional additional extension period for young patients b											Post drug elimination follow-up		Unscheduled
Week (W) a	Transition visit W192/EW1	EW24	EW48	EW72	EW96	EW120	EW144	EW168	EW192	EW216	EOT c	EOT +2W	EOT +4W	Relapse visit
Visit number	EV1	EV2	EV3	EV4	EV5	EV6	EV7	EV8	EV9	EV10	EV11	EV12 d	EV13 d	
Entry procedures														
Informed consents e and assent	X													
Efficacy														
Routine neurologic exams	X	X	X	X	X	X	X	X	X	X	X			X
Brain MRI f	X		X		X		X		X		X			
Safety														
Adverse event reporting g	<----->													
Vital signs h	X	X	X	X	X	X	X	X	X	X	X	X	X	X
Physical examination	X	X	X	X	X	X	X	X	X	X	X	X		
Clinical laboratories i	Every 6 weeks	Every 6 weeks	Every 6 weeks	Every 6 weeks	Every 6 weeks	Every 6 weeks	Every 6 weeks	Every 6 weeks	Every 6 weeks	Every 6 weeks	X	X	X	
Treatments														
Concomitant medications	X	X	X	X	X	X	X	X	X	X	X	X	X	X
Dispense study drugs	X	X	X	X	X	X	X	X	X	X				
Accountability / compliance	X	X	X	X	X	X	X	X	X	X	X			
Teriflunomide PK sampling												X j	X j	

EOT = end of treatment (EOT= First visit after last study drug intake), EV = Extension visit, EW = Extension Week, MRI = magnetic resonance imaging, PK = pharmacokinetic

- a The optional additional extension period starts with a transition visit. It is recommended that there is no time gap between the 2 periods, or as short as possible and if possible less than 2 weeks. Exams do not need to be repeated at entry in the optional additional extension period.
- b For a regional or national emergency declared by a governmental agency, contingency measures are included in [Section 17.7](#)
- c End-of-treatment and premature discontinuation visit. Patients should be seen within 3 months after the switch to commercial product. In case of discontinuation, the patient should be seen as soon as the decision to stop the drug is taken.

- d* For patients prematurely discontinuing treatment, 2 post- drug elimination follow-up visits should be scheduled 2 weeks and 4 weeks after study medication discontinuation and initiation of the drug elimination procedure.
- e* Re-consent before starting optional additional extension period for young patients.
- f* If patient is treated with steroids the MRI should be performed after 14 days discontinuation of the steroids. No central reading for MRI is planned in the optional additional extension period.
- g* During the adverse event reporting process, specific questions about pulmonary symptoms and peripheral neuropathy symptoms will be asked. (Patients will be instructed to alert the treating physician of symptoms suggestive of immunodeficiency).
- h* Including systolic and diastolic blood pressure, heart rate, body temperature, weight and height; patient standing in bare or stocking feet. Height and weight is to be documented in the growth charts –Blood pressure (BP) and heart rate to be measured in both the supine and the standing positions (measures taken 3 minutes after supine and 3 minutes after standing). A sphygmomanometer with a blood pressure cuff appropriate to the patient's arm girth is used. Of note, during remote visits, only weight will be collected.
- i* Standard liver function test and hematology tests to be performed every 6 weeks (specific panel to be decided by Investigator). These tests will be performed in local laboratories. Clinical relevant abnormalities should be reported as TEAEs (Refer to [Section 9.10.2.1](#)). Other data will not be entered in eCRF.
- j* Post drug elimination procedure: samples to be collected for verification of plasma teriflunomide concentrations  $\leq 0.02$   $\mu\text{g/mL}$ .

